6.14 Blinding and Unblinding Methods

In the event of a serious adverse event or other circumstance requiring unblinding, in the opinion of the responsible physician, the site investigator will notify KUMC. The Protocol Investigator at KUMC and the statistician will unblind the subject to the site investigator if necessary. If the treatment blind is broken, the reason and the date should be recorded and signed by the investigator.

6.15 Agent Destruction/Disposal

At the completion of investigation, all unused study agent will be returned to Novartis or destroyed in accordance with each site's investigational pharmacy regulations.

7.0 CLINICAL EVALUATIONS AND PROCEDURES

7.1 Schedule of Events

Study Procedure	Eligibility Period	Treatment Period					4 week follow-up phone contact
	Visit 1 Baseline	Visit 2 On-Study	Monthly Phone Contacts	Visit 3 6 month Visit	Monthly Phone Contacts	Visit 4 12 month visit (optional participation)	
Eligibility Checklist	X						
Informed Consent*	X	X		X		X	
Medical History	X ^o	X ^o					
Breast Exam	X ^o	X ^o		X		X	
Physical Exam	X ^o	X ^o		X		X	
Mammogram	X			X		X	
Ht/Wt/Vital Signs	X	X		X		X	
RPFNA	X			X		X	
CBC, Chemistry, 25-OH vitamin D +	X	X		X		X	
#Fasting blood for: Bioavailable estradiol, testosterone, SHBG, osteocalcin, N-telopeptide, CRP, lipid panel	X			X		X	
#Trough blood (serum) sample				X		X	
Hot flash assessment	X	X	X	X	X	X	X
Fatigue inventory, BCPT Symptom Check List, HAQ Fibromyalgia Impact Questionnaire		X		X		X	
Adverse Events		X	X	X	X	X	X
Dispense Study Agent/Evaluate Compliance		X		X		X	
Concomitant Medication	X	X	X	X	X	X	X
Return Study Agent				X		X	
Off-Study DEXA scan				X	or	X	
Off-Study evaluation							X

*Subjects will sign a consent each time an RPFNA procedure is performed (at KUMC HSC#4601). Only subjects qualifying for the drug/placebo dispensation will sign the study consent document. For sites other than KUMC, they may determine to use the study consent for the screening RPFNA per the site IRB requirements. Subjects will not be officially "on study" until eligibility is determined.

#After a 10-12 hour fast, four gel-clot 7 ml tubes drawn, allowed to clot at room temperature for 30 minutes, spun at 3500 rpm for 15 minutes, and aliquots of serum into 8 polypropylene storage tubes. Tubes to be labeled with subject initials, randomization number and date of draw. Tubes frozen at -80°C and then shipped to KUMC on \geq 5 lbs of dry ice, with pre/post specimens shipped together. Notify KUMC by fax and email prior to shipment.

+CBC, Chemistry, and 25-OH vitamin D to be performed by local laboratory at the expense of site PI (to be included in budget/subject costs)

° Study medical history, breast and physical exams may be done at any point within 3 months prior to randomization and starting study agent. If done prior to Visit 2, any new conditions or changes will be evaluated and documented before randomization and starting study agent.

7.2 Pre-Study Procedures and Evaluations

7.2.1 Pre-study Eligibility RPFNA Procedure Details

RPFNA will be performed, under local anesthesia from both breasts (two sites on each breast) and all cells pooled from both breasts (one breast in the case of prior DCIS or invasive cancer) into a single 15 cc tube containing modified Cytolyt™ (9 cc Cytolyt™ and 1 cc 10% neutral buffered formalin). After cleansing the breast with betadine and alcohol swabs, the breast is anesthetized with epinephrine and lidocaine using a tuberculin syringe. After the surface has been anesthetized, epinephrine and lidocaine are injected deeper into the breast at two sites, approximately at the 10 and 2 o'clock locations. Then, 5-6 needle passes with sterile RPMI prewetted 10-12 cc syringes/with 21 gauge 1 ½ inch needle, within the anesthetic puncture sites to withdraw epithelial cells lining the ductal tree. Clinician will preferentially sample areas in which resistance (density) is appreciated with the tip of the needle. Sample is immediately expelled into a 15 cc plastic tube containing 9 cc of Cytolyt™ (Cytoc Corp) and 1 cc of 10% neutral buffered formalin. Fluid from the Cytolyt™ tube should be drawn into the needle/syringe hub approximately 4x when expelling material into tube solution, and subject cell material should not be expressed against the side of the tube. Tubes are then placed on a tube rocker for approximately 12-24 hours prior to mailing to KUMC.

After the procedure, subjects will have ice packs placed on the breast for 10-15 minutes to control swelling and bleeding. Subjects are then wrapped with gauze cling wrap to create pressure on the puncture sites. A snug bra is also strongly recommended. Subjects are advised to limit strenuous physical activity over the next 24 hours and to report any pain or signs of infection.

Subjects are offered Ativan 1 mg prior to the procedure for anxiety, and analgesics after the procedure in order to control any pain that may occur. These medications are optional. Subjects should also be instructed to eat a full breakfast the morning of the RPFNA, to abstain from vitamin E, NSAIDS and fish oil products for three weeks prior to RPFNA, and if planning on taking Ativan, to have someone with them to drive them to and from the clinic.

Subjects meeting the eligibility criteria from the RPFNA procedure and completing other pre-study procedures will be offered participation in the trial.

7.2.2 Other pre-study eligibility procedures (see Eligibility in section 4.0)

- Risk assessment

- Mammogram not suspicious for cancer, and any follow-up imaging recommended completed and not suspicious for cancer

7.3 Baseline Studies

7.3.1 Brief Physical and Medical History

Subjects will have a brief physical (including clinical breast exam) performed by a study-associated clinician. All abnormal findings will be recorded on the physical source document, including duration and severity. Vital signs, height, and weight. Percent body fat will be recorded for those institutions with appropriate scales in the clinic.

Subject will have a medical history collected by study personnel, including event dates, duration, and severity.

Physical (including clinical breast exam) and Medical History can be performed up to 3 months prior to randomization and starting study agent, but will be confirmed at on-study visit and evaluated.

7.3.2 Bloodwork

Standard CBC/Chemistry (and 25-OH vitamin D for determination of eligibility) will be collected and analyzed in a local CLIA approved lab at the expense of the site investigator. All materials will need to be obtained by individual study site. CBC/Chemistry/25-OH vitamin D may be done at any time up to six weeks prior to day of randomization. Results must be known prior to subject randomization.

Fasting blood (10-12 hour fast) will be collected in four gel-clot serum tubes for a lipid panel, bioavailable estradiol and testosterone, bone turnover markers (osteocalcin and N-telopeptide crosslinks), high sensitivity C-reactive protein, 25-OH Vitamin D and processed, stored and shipped per section 7.0 and 8.0. Assays will be performed centrally by KUMC. Kits and explicit instructions will be provided for this bloodwork by KUMC to individual sites.

An additional 3 cc specimen will be collected for possible letrozole blood levels. See section 7.0 and 8.0 for processing, storage and shipping instructions. Assays will be performed centrally after shipment to KUMC. Kits and explicit instructions will be provided for this bloodwork by KUMC to individual sites.

7.3.3 Baseline symptom assessment

A baseline symptom assessment will be made via the BCPT symptom checklist, including such relevant conditions as hot flashes, menstrual abnormalities, pelvic pain, muscle and joint pain, and fatigue.

We will utilize the hot flash scoring system developed by [name] at Mayo Clinic. For muscle and joint symptoms and function we will use the validated HAQ Fibromyalgia Impact Questionnaire from the Health Assessment Questionnaire (Stanford), and for fatigue the brief fatigue inventory [Wolfe 2004; Mendoza 1999; Loprinzi 2002]. Adverse events will be recorded using NCI common terminology criteria for adverse events version CTCAE 3.0.

7.4 Evaluations During Study Intervention

Monthly Telephone Assessment

Subjects will be contacted by the study coordinator on a monthly basis to review dosing and adverse events. Subjects who are difficult to reach or do not respond to messages and other means of contact may be considered non-compliant. These will be recorded in the source documents and subsequently entered onto CRFs.

7.5 Evaluation at Completion of Randomized Portion of Study at 6 Months (See section 7.1 for Study Calendar)

If necessary for synchronizing scheduling of RPFNA with continued use of letrozole, study agent may be continued for up to one additional month, until the RPFNA is performed. If this occurs, then studies associated with the repeat RPFNA and completion of study will be conducted at that time, not at a calendar six months.

Subjects should NOT take the study drug the day of the procedure and should have blood drawn after a 10-12 hour fast.

Subjects will have a mammogram, RPFNA, CBC/Chem and fasting study bloodwork collected, and a brief physical (including clinical breast exam) performed by a study-associated clinician (see the study calendar, section 7.1 for a comprehensive list). All abnormal findings will be recorded on the physical source document, including duration and severity. Vital signs, height, and weight will be recorded. Percent body fat will also be and percent body fat will also be recorded.

Bloodwork for CBC/Chem (sent to local CLIA lab), fasting (10-12 hour fast) bloodwork and drug trough serum sample will be collected.

Subjects wishing to participate an additional six months in the open label portion of the study will be given an additional 7 month supply and then asked to return for a repeat RPFNA, breast density and other biomarker assays (see study calendar section 7.1).

When the subject has completed taking study agent, any remaining supply will be counted by the study coordinator and recorded, and returned to the Investigational Pharmacy. The assessment of compliance will be performed on the data entered onto the CRF from the pill counts.

When the subject has completed taking study agent, she will receive a DEXA scan to document any effects on bone health.

7.6 Post-intervention Follow-up Period

Approximately two weeks after last consumption of study agent, subject will be contacted by telephone by the trial coordinator to assess adverse events and answer any remaining questions.

8.0 BIOLOGIC SPECIMEN HANDLING, STORAGE AND SHIPPING

All specimens will be placed in polypropylene storage tubes labeled with subject initials and study/randomization number, date of collection and contents of tube.

RPFNA specimens are to be collected as in 7.1.1. Tubes should be placed on a rocker for 12-24 hours to ensure thorough bathing of cells. Tubes containing RPFNA specimens should be overnight shipped with cool packs and using the KUMC Outside RPFNA Shipping Form within 36 hours of collection. The shipping form should also be faxed to [name] in order to notify the KUMC Lab of the shipment. A call to [contact] should also be made to make certain the lab is aware of the shipment.

CBC/Chem specimens and assays of 25,OH-vitamin D for eligibility will be sent to the local CLIA approved lab and the costs covered by the local PI budget.

Study bloodwork should be collected fasting in four gel-clot tubes, allowed to clot at room temperature for 30 minutes, spun for 15 minutes at 3500 rpm, and the serum poured into four polypropylene storage tubes and labeled as in 8.1. These specimens should be immediately frozen and stored at -80°C until shipment to KUMC. All specimens for each subject should be sent together, overnight, on 5 lbs or more of dry ice, in order to be run together. Notification of KUMC via [contact]) and [contact]) must be made to make certain the lab is aware of the shipment.

No specimens should be shipped the day before a holiday or weekend. If it is uncertain whether the KUMC lab will be open, contact them before shipping.

9.0 SAFETY ASSESSMENTS

9.1 Definition of an Adverse Event

An adverse event (AE) is any untoward medical occurrence in a study participant. An AE does not necessarily have a causal relationship with the treatment or study participant. An AE can therefore be any unfavorable and unintended sign (including an abnormal laboratory finding), symptom, or disease temporally associated with participation in a study, whether or not related to that participation. This includes any death that may occur while a participant is on study.

Medical conditions/disease present before starting study treatment are only considered adverse events if they worsen after starting study treatment (any procedures specified in the protocol). For purposes of this study, only those events that occur after a subject is randomized are considered adverse events and should be noted as such. Abnormal laboratory values or test results constitute adverse events only if they induce clinical signs of symptoms or require therapy, and are recorded on the AE CRF under the signs, symptoms or diagnosis associated with them.

9.2 Adverse Event Reporting

9.2.1 Reportable Adverse Events

For this study, only subjects that have signed the study consent **and** have been randomized to study agent will have adverse events recorded.

9.2.2 Adverse Event data elements

- AE onset date
- AE Verbatim Term
- CTCAE Term (version 3.0)
- AE end date
- Severity grade
- Attribution to study agent (relatedness)
- Reported as a Serious Adverse Event (SAE)?
- Action taken with study agent
- Outcome of the event
- Comments

9.2.3 Severity of Adverse Events

Identify the adverse event using the NCI Common Terminology Criteria for Adverse Events (CTCAE) version 3.0. The CTCAE provides descriptive terminology and a grading scale for each adverse event listed. A copy of the CTCAE can be found at <http://ctep.cancer.gov>.

AEs will be assessed according to the CTCAE grade associated with the AE term. AEs that do not have a corresponding CTCAE term will be assessed according to their impact on the participant's ability to perform daily activities as follows:

GRADE	SEVERITY	DESCRIPTION
1	Mild	
 ◆ Barely noticeable, does not influence functioning ◆ Causing no limitations of usual activities
2	Moderate	
 ◆ Makes participant uncomfortable, influences functioning ◆ Causing some limitations of usual activities
3	Severe	
 ◆ Severe discomfort, treatment needed ◆ Severe and undesirable, causing inability to carry out usual activities
4	Life threatening	
 ◆ Immediate risk of death ◆ Life threatening or disabling
5	Fatal	
 ◆ Causes death of the participant

9.3 Assessment of Relationship of AE to Treatment

The possibility that the adverse event is related to study drug will be classified as one of the following: not related, unlikely, possible, probable, definite.

9.4 Follow-up of AEs

All AEs, including lab abnormalities that in the opinion of the investigator are clinically significant, will be followed according to good medical practices and documented as such, until such AEs resolve or become stable in the opinion of the investigator.

9.5 Serious Adverse Events

ICH Guidelines E2A and Fed. Reg. 62, Oct. 7, 1997 define serious adverse events as those events, occurring at any dose, which meet any of the following criteria:

- Results in death
- Is life threatening (note: the term life-threatening refers to an event in which the patient was at risk of death at the time of the event; it does not refer to an event which hypothetically might have caused death if it were more severe).
- Requires inpatient hospitalization or prolongation of existing hospitalization
- Results in persistent or significant disability/incapacity
- Is a congenital abnormality/birth defect
- Events that may not meet these criteria, but which the investigator finds very unusual and/or potential serious, will also be report in the same manner.

9.6 Reporting Serious Adverse Events

9.6.1 Central Reporting

KUMC will report all SAEs to Novartis, Pharmaceuticals Clinical Safety and Epidemiology Department (CS&E). NCI and to the FDA per GCP guidelines. These reports are to be filed utilizing the Form FDA 3500A (MedWatch Form). Documentation of this submission should also be forwarded to Novartis CS&E in a timely manner. The investigator must also notify Novartis CS&E department which of the SAEs has been expedited (15-day submissions) to the FDA, within 24 hours of submission to the FDA.

Novartis CS&E department must be copied on any study related safety information sent to the IRB.

In addition, any serious adverse event regardless of relationship to the study drug, including pregnancy, occurring in a subject after providing informed consent, while receiving study drug, and until four weeks after stopping study drug, must be reported to Novartis Pharmaceuticals CS&E Department by [contact]) within 24 hours of learning of it's occurrence. It is requested that SAEs are reported to Novartis using the Novartis PIND Serious Adverse Event Report form, with clear documentation in the narrative that the PI is the holder of a private IND. The period after discontinuing study drug may be extended if there is a strong suspicion that the drug has not yet been eliminated. All serious adverse events must also be reported for the period in which the study protocol interferes with the standard medical treatment given to a subject (e.g., treatment withdrawal during washout period, change in treatment to a fixed dose of concomitant medication).

All sub-contracted sites must report knowledge and information regarding an SAE to KUMC and the Protocol Chair or her designee within 72 hours of this occurrence via fax, email and/or telephone. A written report must be faxed to KUMC for review and possible submission to Novartis, NCI and/or the FDA, and to the local site IRB.

KUMC [contact]
KUMC [contact]
Attention: [name]
[contact]
Protocol Chair

9.6.2 Include the following information when contacting the Protocol Chair:

- Date and time of the SAE
- date and time of the SAE report
- name of reporter
- call back information
- affiliation/institution conducting the study
- protocol number

- title of protocol
- description of SAE, including attribution to drug and expectedness
- subject randomization number

9.6.3 Follow-up of SAE

Site staff should send follow-up reports as requested when additional information is available. Additional information should be entered on the NCI DCP SAE form in the appropriate format. Follow-up information should be sent to the Protocol Chair at KUMC as soon as possible.

All SAE's will be followed until there is resolution or stability based on the PI's judgment.

10.0 BIOMARKER AND LABORATORY ASSESSMENTS

The RPFNA specimen will be analyzed in the KUMC Breast Cancer Prevention Center Laboratory, under the direction of [name], DVM, PhD. The Breast Cancer Prevention Laboratory and Research Administrative Unit are located in the Lied Research Building. It consists of three laboratory rooms with a total of 1597 square feet plus 1200 square feet of office space. The laboratories are fully equipped for cell culture, the processing and assessment of cytology and immunocytochemistry slides, assay of serum hormones and IGF-1/IGFBP-3, (ELISA's RIAs), laser microdissection, qRT-PCR, and various other molecular biology techniques. Staff located in the administrative/laboratory unit include two cytology/immunochemistry technicians, and an additional technician experienced in performing ELISAs RIA's for hormone assays as well as RTPCR and other molecular assays.

10.1 Ki-67

Breast Cells from RPFNA are pooled in modified cytolyt and sent to KUMC by express mail within 72 hours of RPFNA and all will be processed to slides within 96 hours. Cells are processed to thin prep slides via standard manufacturer's specifications.

A minimum of three slides will be made by a liquid-based cytologic technique: at least one each for cytomorphology, Ki-67 and microdissected prior to RNA extraction. Total epithelial cells will be delineated with Mayer's hematoxylin counterstain and proliferating cells with a MIB-1 antibody for Ki-7. Only baseline slides containing > 500 epithelial cells are processed and stained for Ki-7. Antigen retrieval is performed with 10 nmol/L citrate buffer (pH 6) in a Biocare (Walnut Creek, CA) decloaking chamber for two minutes at 120 degrees C. Slides are then stained with a MIB-1 monoclonal antibody (M7240 Dako Cytomation, Carpinteria, CA) at a 1:20 dilution in a Dako Autostainer [Khan 2005]. Hyperplastic clusters are preferentially assessed and the number of cells with unequivocal nuclear staining out of 500 cells assessed and recorded. Manual counting will be employed and scoring assessed by two laboratory technicians. The scores will consist of number of cells assessed, and number of positive cells for Ki-67. A separate score for each technician and a consensus score will be recorded. The consensus score will be utilized for analysis of the primary endpoint. Representative cell clusters are archived with a digital imaging system.

In the event that fewer than 500 epithelial cells are present in the Ki-67 slide on the follow-up RPFNA, the cytology slide will be destained and used for Ki-67 staining. If there are still less than 500 evaluable cells present when all slide material is combined the post-treatment value for Ki-67 will be considered as the proportion of epithelial cells staining positive for Ki-67 relative to the total number of epithelial cells present. If no staining for Ki-67 is observed and there are less than 500 evaluable cells, the value will be imputed as the reciprocal of the total number of evaluable cells present. If there is no staining and greater than 500 cells, the value will be assumed to be zero. Subjects with less than 100 evaluable cells will be considered not evaluable for Ki-67.

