
Number of subjects: The primary endpoint will be the change in Ki-67 expression at 6 months. Specifically, we will compare this change using a two-sample t-test between subjects randomized to letrozole versus those randomized to placebo. From our pilot study, the average percentage of cells expressing Ki-67 at baseline was 6.4% with an average change of -3.7% with a common standard deviation of 5.5% in subjects meeting the eligibility criteria for this trial. Using a 1 to 1 randomization scheme and presuming mean change for placebo is 0, we will have 90% power to detect a difference of 3.7% in Ki-67 in the letrozole group with a type I error rate of 5% with a total of 96 evaluable subjects. We intend to accrue 108 subjects in order to attain 96 evaluable subjects.

The clinical flow design we will use to satisfy the Specific Aims is as follows:

←Screening period→ -3 to 0 months	← Treatment period → 0-12 months					
VISIT 1 High Risk Postmenopausal Subjects on ERT for > 6 months with stable dose and route DEXA within 2 years Breast Exam, Mammogram (for breast density) RPFNA (cytology, Ki-67) Hyperplasia +/- atypia and Ki-67 >1.5% CBC, chem, 25-OH-D Baseline history/ Breast exam, Physical*	VISIT 2 Day 0 of drug/ placebo dosing	Monthly phone contacts	VISIT 3 Month 6	Monthly phone contacts	VISIT 4 Month 12	OFF STUDY PHONE CONTACT
	Enter study Baseline history/ Breast exam, Physical* bioavailable estradiol, testosterone 25-OH-D Fasting lipid profile Osteocalcin N-teleopeptide Surveys Questionnaires	Trial coordinator contact subject via telephone evaluate AE's, compliance	Repeat baseline studies, return unused study agent or placebo, evaluate AE's, compliance, dispense open label drug DEXA scan if completing study	Trial coordinator contact subject via telephone evaluate AE's, compliance	Repeat baseline studies, return unused study agent, evaluate AE's, compliance DEXA scan	Trial coordinator contact subject via telephone evaluate AE's

***Baseline history, breast exam and physical may be done at any point within 3 months prior to randomization and starting study agent. If done prior to Visit 2, any new conditions or changes will be evaluated and documented before randomization and starting study agent.**

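### Scoring unstained follow-up samples of 100 to 499 cells as 1/n lets a sample with no Ki-67 staining outscore a stained one and slightly understates any letrozole benefit

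*Combined protocol and SAP*

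**What the plan says.** Section 10.1 (Ki-67) sets the scoring of the primary biomarker. The routine score is "the number of cells with unequivocal nuclear staining out of 500 cells assessed and recorded". If the follow-up Ki-67 slide holds fewer than 500 epithelial cells, "the cytology slide will be destained and used for Ki-67 staining", and the material is combined. If the total is still below 500:

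- with some staining, "the post-treatment value for Ki-67 will be considered as the proportion of epithelial cells staining positive for Ki-67", that is k/n;
- with no staining: "If no staining for Ki-67 is observed and there are less than 500 evaluable cells, the value will be imputed as the reciprocal" of the number of evaluable cells, that is 1/n.

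At the two ends of the range: "If there is no staining and greater than 500 cells, the value will be assumed to be zero", and "Subjects with less than 100 evaluable cells will be considered not evaluable for Ki-67".

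Baseline samples are held to a different standard: "Only baseline slides containing > 500 epithelial cells are processed and stained for Ki-7" (the marker name is misprinted there). Section 4.3 also requires baseline Ki-67 of at least 1.5%. The visit table in section 3.0 writes this as "Hyperplasia +/- atypia and Ki-67 >1.5" percent, a difference that does not matter here.

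Section 12.2 compares the change in Ki-67 from baseline to 6 months between arms with a two-sample t-test. It plans no sensitivity analysis for imputed zeros.

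**The concern.** A score for percent positive cells should not give a sample with no positive cells a higher value than a sample with some. The reciprocal rule does this because it applies to one kind of sample only: unstained and below 500 cells. Stained samples of the same size and unstained larger samples get no such adjustment.

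The rule also acts on one side of the change score. A baseline sample must have at least 1.5% positive cells, which is 0.015 × 500 = 7.5 cells in 500, so a zero cannot occur there. Only the post-treatment value can be altered, and always upward. The size of a woman's fall in Ki-67 is then understated. A woman at the entry floor whose follow-up is 0 of 100 is recorded as going from 1.5% to 1.0%, a fall of 0.5/1.5 = 33%, although no cell stained.

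Unstained samples are most likely where Ki-67 has fallen furthest. If letrozole works, that is the letrozole arm, so the estimated treatment difference would be too small. The question is by how much.

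**Working it through.** **Plan's own figure.** Section 12.1 gives a difference of 3.7 points, an SD of change of 5.5, 96 evaluable subjects (48 per arm) and a two-sided 5% t-test. The effect size is 3.7/5.5 = 0.673. The noncentral t distribution with 48 per arm gives 90.4% power, which agrees with the stated 90%.

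**Scores under the rule (no assumptions needed).**

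| Follow-up sample | Score |
|---|---|
| 0/100 | 1.00% |
| 1/100 | 1.00% |
| 1/101 | 0.99% |
| 4/500 | 0.80% |
| 0/200 | 0.50% |
| 2/500 | 0.40% |
| 0/499 | 0.20% |
| 0 of more than 500 | 0 |

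So 0/100 ties with 1/100 and ranks above 1/101 and 4/500, and 0/200 ranks above 2/500. The upward shift per affected sample runs from 100/499 = 0.20 to 100/100 = 1.0 percentage points.

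**Expected bias in a short sample.** With true proportion p and n cells, k/n is unbiased. The rule adds 1/n when k = 0, which has probability (1 − p)^n. The bias is therefore (1 − p)^n / n. For p = 1.6% and n = 100 it is 0.199/100, or 0.20 points. Averaged over n from 100 to 499 with equal weight:

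| True Ki-67 | Mean bias (points) |
|---|---|
| 0 | 0.40 |
| 0.5% | 0.13 |
| 1.6% | 0.021 |
| 5.0% | 0.0003 |

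**Bias in the arm difference.** The documents give no share of follow-up samples below 500 cells, no distribution of cell counts and no rate of zero staining by arm. These are assumptions:

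- Cell counts in short samples are uniform on 100 to 499, alike in both arms and unrelated to Ki-67.
- Follow-up Ki-67 is lognormal, matched to the 33-subject pilot subgroup (sections 2.8 and 12.1). Letrozole has median 1.6% and mean 6.4 − 3.7 = 2.7%, so the log-SD is √(2 ln(2.7/1.6)) = 1.02. Placebo stays at its baseline median of 5.0% and mean of 6.4%, so the log-SD is √(2 ln(6.4/5.0)) = 0.70.
- A share f of follow-up samples is short, with f from 10% to 50%.

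The chance of no staining in a short sample is then 9.9% on letrozole and 0.6% on placebo. The mean bias per short sample is 0.052 and 0.004 points, a gap of about 0.047 points.

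| f | Shrinkage of the difference (f × 0.047) | Power |
|---|---|---|
| 10% | 0.005 | 90.3% |
| 50% | 0.024 | 90.0% |

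**Where it would start to matter.** Suppose half of letrozole subjects truly had no Ki-67 and every short sample had only 100 cells. The shrinkage would be 0.06 points at f = 10% and 0.30 at f = 50%, with power of 89.4% and 85.1%. The outer bound is every letrozole sample at 0 of 100 and no placebo sample affected: 3.7 − 1.0 = 2.7 points and 66% power. Nothing in the documents suggests either situation.

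**The case against.** The rule is prespecified and has a defensible motive. Zero in 100 cells is weaker evidence of a low value than zero in more than 500, so a higher score for the smaller sample follows ordinary detection-limit reasoning. That is right for that pair: it is a jump in the rule, not an inversion. It does not excuse scoring an unstained sample above 4/500.

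Section 10.1 also limits the rule's reach. The cytology slide is destained and pooled first, and only unstained samples of 100 to 499 cells remain affected. That stands, and it is one reason the effect is small.

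Four stronger readings are tempting, and the documents do not support them.

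- A reader might infer that the rule biases the letrozole arm as a matter of fact. That depends on the drug lowering Ki-67. With equal Ki-67 and equal cell yield, both arms are raised alike, so a false positive is not made more likely. If the drug works, the bias is conservative.
- A reader might assume more short samples on letrozole, which would enlarge the bias. No section reports follow-up cell yield by arm.
- A reader might infer that a sample with 0 positive of the standard 500 counted has no score. The thresholds refer to cells present, so a slide holding more than 500 cells scores 0. The gap arises only when the combined material holds exactly 500 cells, a rare case and a wording slip.
- A reader might expect damage to the rank-based fallback in section 12.2. That test applies only under extreme skewness and would rank changes from baseline. In a simulation on the assumptions above, with baseline and follow-up drawn independently, 0.5 to 2.5 subjects per trial were affected and rank-sum power fell by about 0.4 points at most.

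**Conclusion.** The point holds as a minor scoring defect. The ties and inversions follow from section 10.1 alone, and the shift is upward, on the post-treatment value only. Its size rests on the assumed share of short samples and on pilot-matched Ki-67 values. On those terms the planned 3.7-point difference shrinks by less than 1% (0.024/3.7 = 0.6% at most), and power falls from 90.4% to no lower than 90.0%. The sample size needs no change, and the validity of a positive result is not in question. The case for acting is that the error runs one way, is avoidable, and concerns the primary endpoint.

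**What to change.** In section 10.1, replace the two zero-staining sentences with one rule: every follow-up sample with at least 100 evaluable cells is scored as positive cells divided by cells counted, so zero positives scores 0 at any count, including exactly 500. Keep the reciprocal rule only as a sensitivity analysis, and report by arm how many samples it affects.

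No new data are needed, because section 10.1 already records cells assessed and positive cells for each sample. The cost is a one-sentence amendment, which under section 13.0 needs approval by the lead site's IRB and then review at the other sites. It should be settled before unblinding.
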